## 6.1.2. Cryoablation

The cryoablation procedure is conducted with U.S. FDA approved medical devices and disposable probes as an out-patient procedure. Local and/or conscious sedation is allowed. These treatments are used to kill tumor cells. Cryoablation is a minimally invasive treatment that involves placing a probe into a known tumor percutaneously under image guidance (e.g. CT scan or Ultrasound). The cryoablation procedure should be conducted by a licensed interventional radiologist approved by the Sponsor. Unlike normal ablation methods that seek to ablate all viable tumor and leave no tumor at the margins, the ablation procedure for this protocol should aim to ablate only a portion of the tumor and leave viable tumor margins. Effort should be made to ablate viable tumor and avoid necrotic areas of the tumor. Thus, the edge of the tumor, rather than the center is a preferred target. Intratumoral injection of study drug is best accomplished by first inserting a guide device with a gauge larger than the cryoprobe. Generally, a 14g guide is suggested. In this manner, biopsy tools and the cryoprobe can be inserted through the guide to reach the tumor. On site pathology or radiological confirmation that the guide is inserted within viable tumor is preferred. The ablation should occur with at least two freeze-thaw cycles each of at least 10 minutes. The study drug should only be injected when the temperature is verified to be above  $35^{\circ}$  C. The study drug is best delivered using a needle that has side ports to assure the drug is delivered within the ablated lesion and not injected through the lesion into the normal tissue. After the ablation, the guide

tract should be sealed with mesh material to prevent bleeding. All subjects should be observed for at least 2 hours following the procedure for any signs of bleeding or other adverse events. Subjects should be monitored continuously for pulse, respiration, blood pressure and oxygen saturation during the procedure. The type of probes used, the location of the tumor, the amount of tumor ablated, the cooling and warming cycle times, vital signs and procedure notes should be documented in source medical records.

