In accordance with the 3+3 design, three subjects will be accrued into the first dosing schedule. If during the priming, vaccination and activation steps no ADLT are observed in any of the three subjects, accrual into the next cohort is allowed. If an ADLT occurs in two of the three subjects, no further dosing is allowed. If ADLT occurs in one of the three subjects, three additional subjects will be accrued into the same cohort. If no ADLT occurs within the additional three subjects, accrual into the next cohort can begin. If an ADLT is observed in any of the additional three subjects, no further dose escalation is permitted.

The development of any DLT toxicity in  $\geq$  33% of the accumulated number of subjects in any and all dosing schedules during the Safety Evaluation Period will result in protocol discontinuation.

At the completion of the Safety Evaluation Period for all cohorts, the safety evaluation of Part 1 will be considered completed and all enrollment will be closed. Efficacy evaluation will continue monthly for each subject until death or loss to follow-up.

# Part 2

The safety and efficacy data from Part 1 will be evaluated and the favored schedule advanced to Part 2. In Part 2 of the trial, up to 25 additional subjects may be accrued.

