In order to determine the utility of RECIST in evaluating response of patients to immunotherapy, RECIST 1.1 [82] guidelines will be used to determine objective tumor response. This endpoint will be determined and analyzed for correlation with OS. Malignant tumor masses (target lesions) will be selected on the basis of their size and their suitability for accurate repetitive measurements. All patients must have at least one target lesion that can be accurately measured in at least one dimension (longest diameter to be recorded) greater than or equal to 1.0 cm with spiral CT scan. To assess objective response, it is necessary to estimate the overall tumor burden at baseline and use this as a comparator for subsequent measurements. Whenever possible, several measurable lesions, up to a maximum of 2 lesions per organ and 5 total target lesions representative of involved organs, should be identified, measured and recorded at baseline. To allow later retrieval, lesions should be clearly marked on the films or otherwise identified. If the lesion is detected by more than one method at baseline, the investigator should select at baseline the method to be used at subsequent evaluations. All measurements should be performed using a caliper or ruler and should be recorded in metric notation in centimeters. A sum of the longest diameter for all target lesions will be calculated and reported as the baseline sum longest diameter. The baseline sum longest diameters will be used as reference to further characterize the objective tumor response of the measurable dimension of the disease by repeated assessment of the sum of the longest diameters during treatment.

All other lesions (or sites of disease) should be identified as non-target lesions and should also be recorded at baseline. Measurements are not required and these lesions should be followed as "present" or "absent". All baseline evaluations should be performed as closely as possible to the treatment start and never more than 14 days before the beginning of the treatment.

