## **19. APPENDICES**

#### **APPENDIX 1** BIOPSY, CRYOABLATION SURGICAL PROCEDURE

Subjects will be referred to a sponsor dedicated radiology center for the cryoablation and voluntary biopsy procedures and intratumoral injections.

Preferably, the lesion selected for biopsy will not be the same lesion as is targeted for ablation. However, if a second lesion is not available then the lesion for ablation will be biopsied prior to ablation. The cryoablation and biopsy procedures are conducted under CT and/or ultrasound guidance. Visual documentation of probe placement for the cryoprobe probe will be provided and placed in the source documents. In addition, visual documentation of the kill zone after the ablation will also be provided for cryoablation. The tumor biopsy specimen will be placed in formalin in a pre-labeled specimen container. The tumor biopsy specimen will be sent to the Sponsor for pathological analysis.

Subjects will have a target tumor lesion cryoablated under local or conscious sedation followed by an intratumoral AlloStim® injection at a dose of  $1 \times 10^7$  cells formulated in 1 ml of Plasma-LyteA/1% HAS or  $3 \times 10^7$  cells formulated in 3 ml of Plasma-LyteA/1% HSA. The intent of the ablation procedure is not to completely ablate the target lesion, but only to cause an area of necrosis within the tumor. Therefore, it is not necessary to have perfect margins. The intratumoral injection will occur after the ablation area has warmed to  $37^{\circ}$ C.

It is preferred that an interventional radiologist, CT technician, and physician trained in anesthesia or emergency medicine be present during the procedure. A Registered Nurse (RN), medical assistant and a cryoablation technician should also be present to support these procedures (same individual may function in two of these roles). The Sponsor may also have a medical/scientific consultant present. If the ablation target is in or near the lungs, it is recommended that the procedure be conducted in a hospital or near a hospital with the capability to diagnose and treat pneumothorax or related complications.

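### Section 9.2 does not keep the lesion cryoablated and injected on Day 21 out of the RECIST sum, so in A-1 subjects with one or two target lesions the procedure itself can change the sum, in either direction.

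*Combined protocol and SAP*

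**What the plan says.** **Selecting and summing target lesions (Section 9.2).** The criterion is: "Malignant tumor masses (target lesions) will be selected on the basis of their size and their suitability for accurate repetitive measurements". The minimum is one: "All patients must have at least one target lesion that can be accurately measured in at least one dimension". The maximum is "up to a maximum of 2 lesions per organ and 5 total target lesions representative of involved organs". The measure is the sum over all of them: "A sum of the longest diameter for all target lesions will be calculated and reported as the baseline sum longest diameter". The section does not mention a lesion that is treated locally on study.

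**The local treatment.** In Section 8, A-1 subjects have cryoablation and an intratumoral injection on Day 21, while A-2 subjects receive an intravenous dose that day. Section 6.1.2 makes the ablation partial by design: "the ablation procedure for this protocol should aim to ablate only a portion of the tumor". Section 10.2 (criterion 4) requires only one accessible liver lesion for a cryoablation schedule and accepts extrahepatic disease without requiring it.

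**The only separation of lesions.** Section 11.2.4 says in parentheses that the target lesion chosen for biopsy is not the one to be ablated. Appendix 1 makes this a preference and adds: "if a second lesion is not available then the lesion for ablation will be biopsied prior to ablation". Both statements concern biopsy. Section 12.2 and Appendix 1 also call the lesion to be ablated a target lesion, so the term carries two meanings.

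**Use of the data.** CT is read at baseline and Day 91. RECIST is exploratory and is to be correlated with overall survival (Section 9.2). For the choice of schedule, Section 8 (Part 2) says: "The safety and efficacy data from Part 1 will be evaluated and the favored schedule advanced to Part 2". Section 7.1 asks for the schedule with the best efficacy and fewest adverse events. Neither names an efficacy measure.

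**The concern.** RECIST reads a change in the sum of diameters as a change in disease. Section 9.2 itself describes that assumption and doubts it for immunotherapy. Freezing a lesion breaks it in a further way: the size of that lesion at Day 91 partly reflects tissue destruction and repair. Section 11.2.4 lists edema, coagulative necrosis and fibrosis among the causes of enlargement that are not tumor growth.

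The scientific question is whether an in-situ vaccine acts on disease elsewhere. If the treated lesion is in the sum, a local effect of the procedure is counted as part of the answer, and this can happen in A-1 only. At stake are the meaning of the A-1 RECIST and irRC results, the RECIST–survival correlation, and any comparison of A-1 with A-2 that uses these measures.

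**Working it through.** **Can the ablated lesion be a target?** Take the rules as written.
- Section 9.2 selects on size and measurability and needs at least one target.
- Section 10.2 needs at least one accessible liver lesion for A-1.
- No section removes that lesion from the RECIST set.

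So the lesion may be a target. In a subject with no other measurable lesion, it must be. Because of the cap "up to a maximum of 2 lesions per organ", a subject with liver-only disease has at most two targets, so the one- and two-target cases follow from the plan's own rules.

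**How far must it change to move the category?** The protocol gives no figure to reproduce and prints no percentage cut-offs. I assume a 30% fall for response and a 20% rise for progression, with all other targets stable.

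Let *w* be the ablated lesion's share of the baseline sum, *d* its relative change and *T* the change in the sum. Then *T* = *w* × *d*, so *d* = *T* / *w*. With *k* equal targets, *w* = 1/*k* and *d* = *k* × *T*.

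| Equal targets | Fall needed for −30% | Rise needed for +20% |
|---|---|---|
| 1 | 30% | 20% |
| 2 | 60% | 40% |
| 3 | 90% | 60% |
| 4 | 120% (impossible) | 80% |
| 5 | 150% (impossible) | 100% |

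Check with two 40 mm targets (an assumed size):
- 60% shrinkage of one: (40 × 0.4 + 40) / 80 − 1 = 56/80 − 1 = −30%.
- 40% enlargement of one: (40 × 1.4 + 40) / 80 − 1 = 96/80 − 1 = +20%.

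A lesion cannot shrink by more than 100%, so with unequal sizes the ablated lesion must be at least 30% of the baseline sum before it can produce a −30% call alone.

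**What would that do with three subjects per schedule?** This step applies only if RECIST response is used to compare the schedules. Let *q* be the assumed chance that ablation alone creates an apparent response in an A-1 subject. If the true response rate is 0% in both schedules, P(A-1 shows more responders than A-2) = 1 − (1 − *q*)³:
- *q* = 10%: 1 − 0.9³ = 27.1%
- *q* = 25%: 1 − 0.75³ = 57.8%
- *q* = 50%: 1 − 0.5³ = 87.5%

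If the true rate is 5% in both, the A-1 rate is 1 − 0.95 × (1 − *q*). Summing the binomial probabilities over all outcomes with more A-1 than A-2 responders gives 12.3% at *q* = 0 (and 12.3% the other way), then 32.9%, 57.5% and 83.9% at *q* = 10%, 25% and 50%. With the lesion left out, its direct contribution is zero and the chances are equal again.

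The values of *q* are illustrative; the documents give no basis for choosing one. Enlargement at Day 91, which is 91 − 21 = 70 days after ablation, would work against A-1 instead.

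**The case against.** **The criterion may already exclude it.** A reader could judge a lesion due to be frozen unsuitable for repeated measurement, and Section 9.2 cites the RECIST 1.1 guideline, which may cover locally treated lesions. The first is a possible reading, not a rule, and a reader following it would find nothing on a subject with one lesion. The guideline is not available to this review, so nothing is claimed about it. The protocol's own text should settle the point.

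**Section 11.2.4 shows that a distinction was intended.** It does, but for biopsy, and Appendix 1 softens it.

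**Appendix 1 does not show that one-lesion subjects will be enrolled.** This stands. Its second lesion is one available for biopsy, and a subject could have other measurable lesions that are not biopsied. How often the ablated lesion would be the only or main target is unknown.

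**The magnitude rests on assumptions.** This stands too. Cut-offs, lesion sizes and changes are assumed. Ablation is deliberately partial, three equal targets would need a 90% fall, and four or five rule out a 30% fall.

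**The choice of Part 2 schedule.** A reader might infer that the plan biases this choice. The documents do not support that. Sections 7.1 and 8 name no efficacy measure, RECIST is exploratory, the abstract calls the CT analysis experimental, and Section 11.2.4 calls RECIST unreliable here. The link is conditional. It is not excluded either, because Section 11.2.4 also says that radiological endpoints will serve to assess tumor response.

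**Three against three is uninterpretable anyway.** No RECIST test is planned, and such a contrast is weak with or without this lesion. But the RECIST–survival correlation is affected in A-1 whatever drives the choice, and weak data are no reason to leave a removable artefact in them.

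**Conclusion.** The gap is real and the point holds in limited form. As written, the plan allows, and in a subject with no other measurable lesion requires, a lesion frozen and injected on Day 21 to enter the A-1 sum. In subjects with one or two targets, plausible numbers of the kind tabulated above are enough for the procedure to cross an assumed cut-off. With more targets the effect weakens, and for response it disappears at four equal targets.

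The result is contamination of the exploratory RECIST and irRC findings and of the RECIST–survival correlation in A-1. A-1 and A-2 become non-comparable on tumor response if RECIST or irRC enters the Part 1 efficacy evaluation. The documents do not establish the direction or size of the ablation effect, the number of subjects affected, or any effect on the Part 2 choice. The primary safety endpoint is untouched.

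**What to change.** 1. State in Sections 9.2 and 11.2.4 that the lesion planned for ablation or injection is identified and measured at baseline, is left out of the main RECIST sum and the irRC burden, and is reported separately as local effect. Give the sum including it as a sensitivity result.
2. Align the Section 9.2 sentence requiring at least one target lesion. A subject whose only measurable lesion is the ablated one is not evaluable for the main response analysis, appears only in the sensitivity result, and stays in the safety and survival analyses.
3. Reconcile the term target lesion across the Histopathology Assessment in the abstract, Sections 9.2, 11.2.4 and 12.2, and Appendix 1, using separate terms for the lesion measured for RECIST, the lesion biopsied and the lesion ablated.
4. If RECIST or irRC is meant to inform the choice of Part 2 schedule, say so in Section 8 and specify the version without the ablated lesion.

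The cost is a few sentences in those sections and in the reader instructions. Section 12.2 already has the interventional radiologist identify and describe the lesion at screening, so it can be marked before the baseline read. No dose, procedure or sample size changes. The downside is that a few A-1 subjects may be non-evaluable for the main RECIST analysis, which is noticeable in a cohort of three; the sensitivity result keeps their data visible.

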# **10. SELECTION OF SUBJECTS**

#### **10.1.** NUMBER OF SUBJECTS

Approximately 6 subjects will be enrolled in the dose schedule evaluation Part 1 of the trial. In Part 2 of the trial, up to 25 additional subjects may be accrued in the one of the dose schedules. Recruitment Methods

Efforts will be made to include all eligible subjects in this study. Subjects will be recruited from a population of patients who have been previously evaluated at the participating institution or have been referred from other institutions. The subject's medical record will be reviewed by the investigator to determine his/her eligibility for the study.

Each subject or subject's legally acceptable representative must sign a current Institutional Review Board (IRB) approved Informed Consent Form (ICF) before any study-related procedures are performed.

# **10.2.** INCLUSION CRITERIA

- 1. Adult males and female subjects aged 18-80 years at screening visit
- 2. Pathologically confirmed diagnosis of colorectal adenocarcinoma

- 3. Presenting with metastatic disease:
  - Primary can be intact or previously resected
  - Metastatic lesion(s) in liver must be non-resectable
  - Extrahepatic disease acceptable
- 4. At least one liver lesion able to be visualized by ultrasound and determined to be safely assessable for percutaneous cryoablation (if schedule includes cryoablation)
- 5. Previous treatment failure of two previous lines of active systemic chemotherapy:
  - Previous chemotherapy must have included an oxaliplatin-containing (e.g. FOLFOX) and an irinotecan-containing (e.g. FOLFIRI) regimen
    - With or without bevacizumab
    - o Administered in adjuvant setting or for treatment of metastatic disease
    - If KRAS wild type, must have at least one prior anti-EGFR therapy
    - Treatment failure can be due to disease progression or toxicity
    - o Disease progression on second line therapy must be documented radiologically and must have occurred during or within 30 days following the last administration of treatment for metastatic disease
- 6. ECOG performance score: 0-1
- 7. Adequate hematological function:
  - Absolute granulocyte count  $\geq 1,200/\text{mm}^3$
  - $\circ$  Platelet count > 100.000/mm^3
  - $\circ$  PT/INR  $\leq$  1.5 or correctable to <1.5 at time of interventional procedures
  - Hemoglobin  $\geq 9 \text{ g/dL}$  (may be corrected by transfusion)
- 8. Adequate Organ Function:
  - $\circ$  Creatinine  $\leq 1.5 \text{ mg/dL}$
  - Total bilirubin  $\leq 1.5$  times upper limit of normal (ULN)
  - Alkaline phosphatase  $\leq 2.5$  times ULN \*
  - Aspartate aminotransferase (AST) or (SGOT)  $\leq$  2.5 times ULN \*
  - Alanine aminotransferase (ALT) or (SGPT) < 2.5 times ULN \*

\*or <5x ULN if liver involvement

- 9. EKG without clinically relevant abnormalities
- 10. Female subjects: Not pregnant or lactating
- 11. Patients with child bearing potential must agree to use adequate contraception
- 12. Study specific informed consent in the native language of the subject.

# **10.3.** EXCLUSION CRITERIA

- 1. Bowel obstruction or high risk for obstruction
- 2. Moderate or severe ascites requiring medical intervention
- 3. Clinical evidence or radiological evidence of brain metastasis or leptomeningeal involvement
- 4. Symptomatic asthma or COPD
- 5. Pulmonary lymphangitis or symptomatic pleural effusion (grade  $\geq 2$ ) that results in pulmonary dysfunction requiring active treatment or oxygen saturation <92% on room air

- 6. Bevacizumab (Avastin®) treatment within 6 weeks of scheduled cryoablation procedure (if schedule includes cryoablation)
- 7. Regorafenib prior to the Study Period
- 8. Previous treatment with TAS102
- 9. Any of the following mood disorders: active major depressive episode, history of suicidal attempt or ideation
- 10. Taking anticoagulant medication for concomitant medical condition (unless can be safely discontinued for invasive cryoablation, biopsy and intratumoral injection procedures)
- 11. Prior allogeneic bone marrow/stem cell or solid organ transplant
- 12. Chronic use (> 2 weeks) of greater than physiologic doses of a corticosteroid agent (dose equivalent to > 5 mg/day of prednisone) within 30 days of the first day of study drug treatment
  - Topical corticosteroids are permitted
- 13. Prior diagnosis of an active autoimmune disease (e.g., rheumatoid arthritis, multiple sclerosis, autoimmune thyroid disease, uveitis). Well controlled Type I diabetes allowed
- 14. Prior experimental therapy
- 15. History of blood transfusion reactions
- 16. Known allergy to bovine products
- 17. Progressive viral or bacterial infection
  - All infections must be resolved and the subject must remain afebrile for seven days without antibiotics prior to being placed on study
- 18. Cardiac disease of symptomatic nature
- 19. History of HIV positivity or AIDS
- 20. Concurrent medication known to interfere with platelet function or coagulation (e.g., aspirin, ibuprofen, clopidogrel, or warfarin) unless such medications can be discontinued for an appropriate time period based on the drug half-life and known activity (e.g., aspirin for 7 days) prior to cryoablation and biopsy procedures
- 21. History of severe hypersensitivity to monoclonal antibody drugs or any contraindication to any of the study drugs
- 22. Psychiatric or addictive disorders or other condition that, in the opinion of the investigator, would preclude study participation.
- 23. Subjects that lack ability to provide consent for themselves

# **11. STUDY PLAN AND PROCEDURES**

# 11.1. OVERALL STUDY PLAN

Subjects will be screened for eligibility for the study. The screening process involves examining medical records to determine eligibility based on the IC/EC criteria. After obtaining informed consent, subjects will undergo physical exam, provide blood for lab analysis (CBC, CMP, total IgG and IgM, lipase, erythrocyte sedimentation rate, and CRP), an ultrasound of the liver, and a CT scan. The results of these baseline tests will be reviewed by the Principal Investigator (PI) and the Sponsor's medical monitoring team to determine if the subject still meets IC/EC. In schedule A-1, the study interventional radiologist will determine if the subject has a lesion assessable for cryoablation. If the subject meets IC/EC criteria, a biopsy and tumor harvest procedure will be conducted.

When the PI and the Sponsor agree that all IC/EC criteria are met, the subject is accrued/ enrolled in the study and assigned a protocol number. The enrollment date will be documented in CRF/eCRF. Upon accrual, the study site develops an appointment schedule for the subject and sends to the Sponsor for approval. Upon approval, the subject is notified of the schedule. The Sponsor will produce and ship AlloStim® in accordance with the approved schedule.

AlloStim® will be formulated in Israel by the Sponsor, packaged in validated temperaturecontrolled container and delivered by specialized courier service to the study site at least one day before the established treatment schedule day. AlloStim® is stable in formulation for at least 72 hours. All protocol required CT scans will be conducted at a radiology center. Cryoablation, intratumoral AlloStim® and voluntary tumor biopsies will be conducted at a radiology center.

